After the last subject in the primary Study SHP607-202 has completed the last study visit, an interim analysis for Study SHP607-203 will be performed for all enrolled subjects who have either completed the 24 months CA visit assessments or prematurely withdrawn from Study SHP607-203, and after all associated data have been entered into the database with queries and discrepancies resolved.

STUDY SCHEDULE

Table 1 Schedule of Assessments

Table 1 Schedule of Assessments

Procedures ^a	Initial Study Visit	Months (CA)				Years (CA)				
		12 mo +2 wk ^b	18 mo ±6 wk	24 mo ±6 wk	30 mo ±6 wk	3 yr ±6 wk	3.5 yr ±6 wk	4 yr ±6 wk	4.5 yr ±6 wk	5 yr ±6 wk /ET
	Clinic	Phone	Clinic	Phone	Phone	Phone	Phone	Phone	Phone	Clinic
Medications, procedures, therapies	•	•	•	•	•	•	•	•	•	•
Adverse events ^j	•	•	•	•	•	•	•	•	•	•

ADHD-RS=Attention-Deficit/Hyperactivity Disorder Rating Scale; BSID=Bayley Scales of Infant and Toddler Development; CA=corrected age; CIQ=Caregiver Impact Questionnaire; EQ-5D-5L=EuroQol 5-dimensional 5-level descriptive system; GMFM=Gross Motor Function Measure; ET=early termination; HCRU=health care resource use; HUI2/HUI3=Health Utilities Index Mark 2 and Mark 3; KSPD=Kyoto Scale of Psychological Development; mo=months; MRI=magnetic resonance imaging; PedsQL™=Pediatric Quality of Life Inventory; SCQ=Social Communication Questionnaire; VABS=Vineland Adaptive Behavior Scales; wk=weeks; WPPSI=Wechsler Preschool and Primary Scale of Intelligence

- ^a Visits at 12 months, 24 months, and 5 years CA will be conducted in clinic; all other visits can be conducted by telephone. Assessments at 24 months and 5 years CA may be completed over more than one visit, if needed.
- ^b The initial visit in Study SHP607-203 should coincide with the final visit of the primary Study SHP607-202 at 12 months CA +2 weeks. If the initial visit in Study SHP607-203 does not occur at the 12-month CA visit, the subject may still be enrolled until 24 months CA +6 weeks. Subjects enrolling between the 12 months CA visit and the 24 months CA visit should complete all 12-month CA assessments, and vision and hearing assessment history. Subjects enrolling at the 24 months CA visit should complete informed consent, eligibility criteria, demographics, medical history, and all 24 months CA assessments. Subjects are no longer eligible to enroll in this study after 24 months CA +6 weeks. Completion of Study SHP607-202 is not required for enrollment into Study SHP607-203.

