A number of therapies such as corticosteroids and diuretics are used in the management of BPD in clinical practice; however, there is insufficient evidence supporting the use of many of these agents and no single therapy has been shown to have a significant impact on the incidence or severity of BPD ([Iyengar and Davis, 2015](#)). The majority of the drugs studied in randomized, controlled studies failed to reduce the incidence of BPD. No pharmacologic therapies are currently indicated for the prevention or treatment of BPD. IGF-1 was recognized as one of the potential novel therapies for BPD during the recent NICHD Workshop on BPD ([Higgins et al., 2018](#)).

Chronic respiratory morbidity (CRM) after discharge from the Neonatal Intensive Care Unit (NICU) is a common adverse outcome of premature birth resulting in recurrent respiratory symptoms requiring treatment with pulmonary medications such as bronchodilators, need for supplementary home oxygen, frequent emergency room visits or hospital readmissions, especially during the first 2 years of life ([Ali and Greenough, 2012](#)). However, there is currently insufficient or conflicting evidence that the use of oxygen at term equivalence consistently predicts the later development of CLD in children born extremely premature. Extremely preterm infants diagnosed with BPD often continue to live with impaired lung or respiratory function after discharge from neonatal intensive care and put additional burden on health care systems with increased use of direct and indirect medical care that persists into infancy, school-age, adolescence, and possibly adulthood ([Bhandari and McGrath-Morrow, 2013](#)). The Prematurity and Respiratory Outcomes Program (PROP) study showed that 46-69% of extremely preterm infants had persistent respiratory morbidity, based on assessment of factors such as hospitalization, home support, and medications ([Keller et al., 2017](#)). Their lung function abnormalities may further increase their susceptibility for chronic obstructive pulmonary disease as they age ([Filippone et al., 2009](#); [Fakhoury et al., 2010](#); [Fawke et al., 2010](#); [Bhandari and McGrath-Morrow, 2013](#)).

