Study SHP607-202 is a Phase 2b, multicenter, randomized, open-label, controlled, 3-arm study that is being initiated to evaluate the clinical efficacy and safety of SHP607 in preventing chronic lung disease through 12 months CA compared to standard neonatal care in extremely premature infants. Approximately 477 subjects with GA of 23 weeks +0 days to 27 weeks +6 days will be randomized in a 1:1:1 ratio to receive either SHP607 at 250 µg/kg/24 hours, SHP607 at 400 µg/kg/24 hours, or standard neonatal care alone. Subjects randomly assigned to treatment will receive continuous IV infusion of study drug commencing within 24 hours of birth, once all baseline assessments have been completed. The infusion of study drug will continue to PMA 29 weeks +6 days. The primary objective of the study is to assess the effect of SHP607 on reducing the burden of CLD, as indicated by a reduction in time to final weaning off respiratory technology support (RTS) through 12 months CA, as compared to a standard neonatal care group.

Study SHP607-202 will evaluate the clinical efficacy and safety of SHP607 in preventing chronic lung disease through 12 months CA compared to standard neonatal care in extremely premature infants. Although treatment with SHP607 in Study SHP607-202 represents a short-term exposure (<2 months for each subject), SHP607 may have long-lasting effects on respiratory outcomes as well as other potential outcomes related to complications of prematurity such as neurodevelopment, vision, and growth impairments. In addition, it is critical to understand any long-term safety effects from short-term exposure to SHP607. The purpose of Study SHP607-203 is to evaluate the long-term safety and efficacy outcomes in subjects who received short-term treatment with SHP607 in Study SHP607-202.

The assessment tools used in this study will be different from those used in Study SHP607-202, given the changes in physical and cognitive development that will occur in the subjects as they age during their participation in this study.

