3. STUDY DESIGN

3.1 Study Design and Flow Chart

This is a Phase 2b, multicenter, long-term outcomes study of subjects who were randomized in Study SHP607-202 to either treatment (received SHP607) or control (received standard neonatal care) groups. Subjects will be followed from 12 months CA through 5 years CA. Subjects will not be excluded from participating in other clinical studies. No investigational product will be administered in this study.

Approximately 477 subjects who previously received SHP607 or standard neonatal care in Study SHP607-202 are planned to be enrolled in Study SHP607-203. Although all subjects randomized into the primary Study SHP607-202 (approximately 477) are eligible to enroll in Study SHP607-203, the actual number of subjects enrolled will more closely approximate the number of subjects who complete Study SHP607-202. No investigational product will be administered in Study SHP607-203. A total of approximately 382 subjects (approximately 127 subjects randomized to SHP607 250 µg/kg/24 hours, approximately 127 subjects randomized to SHP607 400 µg/kg/24 hours, and approximately 127 subjects randomized to standard neonatal care) are expected to complete Study SHP607-202. At 12 months CA, subjects will be eligible to enroll into the long-term outcome Study SHP607-203.

[figure not shown]
For subjects who complete the primary Study SHP607-202, the initial visit in Study SHP607-203 should coincide with the final visit of Study SHP607-202 at 12 months CA +2 weeks. If the initial visit in Study SHP607-203 does not occur at the 12-month CA visit, the subject may still be enrolled until 24 months CA +6 weeks. Subjects enrolling between the 12 months CA visit and the 24 months CA visit should complete all 12-month CA assessments, and vision and hearing assessment history. Subjects enrolling at the 24 months CA visit should complete informed consent, eligibility criteria, demographics, medical history, and all 24 months CA assessments. Subjects are no longer eligible to enroll in this study after 24 months CA +6 weeks. Completion of Study SHP607-202 is not required for enrollment into Study SHP607-203.

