8. ADVERSE AND SERIOUS ADVERSE EVENTS ASSESSMENT

8.1 Definition of Adverse Events, Period of Observation, Recording of Adverse Events

According to the International Conference on Harmonization (ICH), an AE is "any untoward medical occurrence in a patient or clinical investigation subject administered a pharmaceutical product and which does not necessarily have a causal relationship with treatment. An AE can therefore be any unfavorable and unintended sign (including an abnormal laboratory finding), symptom, or disease temporally associated with the use of a medicinal (investigational) product, whether or not related to the medicinal (investigational) product" (ICH Guidance E6 [R2] 2016).

In this long-term outcome study in follow-up to Study SHP607-202, no investigational product is being administered; it is therefore a non-interventional study. However, it seeks information on whether prior administration of IMP in Study SHP607-202 impacts long-term outcomes.

For the purposes of this study only the following AEs will be collected:

- Specified targeted medical events (Section 8.1.4)
- AEs related to investigational product
- AEs leading to withdrawal from the study
- Serious AEs that occur during the study period or were previously present and worsen during the study period.

All AEs described above are collected from the time the informed consent is signed until the defined follow-up period stated in Section 3.2. Where possible, a diagnosis rather than a list of symptoms should be recorded. If a diagnosis has not been made, then each symptom should be listed individually. All AEs described above should be captured on the appropriate AE pages in the CRF and in source documents.

All AEs must be followed to closure (the subject's health has returned to his/her baseline status or all variables have returned to normal), regardless of whether the subject is still participating in the study. Closure indicates that an outcome is reached, stabilization achieved (the investigator does not expect any further improvement or worsening of the event), or the event is otherwise explained. When appropriate, medical tests and examinations are performed so that resolution of event(s) can be documented.

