8.2.3 Serious Adverse Event Definition

An SAE is any untoward clinical manifestation of signs, symptoms or outcomes (whether considered related to investigational product or not and at any dose:

- Results in death
- Is life-threatening. Note: The term “life-threatening” in the definition of “serious” refers to an event in which the subject was at risk of death at the time of the event; it does not refer to an event which hypothetically might have caused death if it was more severe.
- Requires inpatient hospitalization or prolongation of existing hospitalization. Note: Hospitalizations, which are the result of elective or previously scheduled surgery for pre-existing conditions, which have not worsened after initiation of treatment, should not be classified as SAEs.
- For example, an admission for a previously scheduled ventral hernia repair would not be classified as an SAE; however, complication(s) resulting from a hospitalization for an elective or previously scheduled surgery that meet(s) serious criteria must be reported as SAE(s).
- Results in persistent or significant disability/incapacity
- Is an important medical event. Note: Important medical events that may not result in death, be life-threatening, or require hospitalization may be considered an SAE when, based upon appropriate medical judgment, they may jeopardize the subject and may require medical or surgical intervention to prevent 1 of the outcomes listed in this definition. Examples of such medical events include:
 - Bronchospasm associated with anaphylaxis requiring intensive treatment in an emergency room or at home; blood dyscrasias or convulsions that do not result in inpatient hospitalization.
 - Reviewed and confirmed seroconversion for human immunodeficiency virus (HIV), hepatitis A virus (HAV), hepatitis B virus (HBV), hepatitis C virus (HCV), hepatitis E virus (HEV), or parvovirus B19 (B19V)

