3. INVESTIGATIONAL PLAN

3.1 Overall Study Design and Plan

This is a Phase 2b, multicenter, long-term outcomes study of subjects who were randomized in Study OHB-607-202 (previously known as SHP607-202) to either treatment (received OHB-607 [previously known as SHP607]) or control (received standard neonatal care) groups. Subjects are followed from 12 months CA through 5 years CA. Subjects are not excluded from participating in other clinical studies. No investigational product is administered in this study. Approximately 477 subjects who previously received OHB-607 or standard neonatal care in Study OHB-607-202 were planned to be enrolled in Study SHP607-203. Although all subjects randomized into the primary Study OHB-607-202 (approximately 477) are eligible to enroll in Study SHP607-203, the actual number of subjects enrolled would more closely approximate the number of subjects who complete Study OHB-607-202 (a total of approximately 382 subjects). The study designs are presented in Figure 1.

Figure 1 Study Design Flow Diagram

CA=corrected age; D=days; GA=gestational age; IV=intravenous; M=months; W=weeks; Y=years. Visits conducted at the study site are indicated in blue. Visits conducted by telephone are indicated in red.

In the Protocol Amendment 2 of Study OHB-607-202, the study design was updated to include a follow-up period until 24 months CA. As a result the sponsor decided to terminate Study SHP607-203.. The number of subjects enrolled in this study is less than 10% of the planned number, and few subjects completed the study (i.e. completed 5-year CA assessments). Thus, only sponsor-designated safety data will be analyzed and reported in this early-terminated study.

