The number and percentage of subjects reporting AEs, as well as the number of events (except for tables by the maximum severity), in each treatment group and overall will be tabulated, respectively, in following ways:

- By system organ class (SOC) and PT for all AEs
- By the maximum severity, SOC and PT for all AEs
- By SOC and PT for all AEs considered related to IP as administered in Study OHB-607-202
- By SOC and PT for all AEs considered related to study procedures
- By SOC and PT for all AEs leading to death
- By SOC and PT for all AEs leading to study discontinuation
- By SOC and PT for all SAEs
- By risk term, seriousness, and relationship to antecedent IP for AEs of important potential risks
- Most frequent AEs by PT (sorted by frequency, occurring in $\geq 5\%$ of subjects in any treatment arm)

In tables by severity or relationship, missing severity or missing relationship imputation will be applied, and handling of those missing cases are detailed in Section [9.2.2](#) and [9.2.3](#), respectively. If a subject had multiple occurrences of the same AEs, the subject will be counted only once per SOC and once per PT at the maximum severity. Handling of incomplete AE start/end dates is described in Section [9.2.1](#).

All AEs will be presented in a data listing. Separate data listings will be presented for AEs related to the antecedent IP, AEs related to study procedures, AEs leading to death, SAEs and AEs of important potential risks.

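### SAP 7.1 pools adverse events from consent to exit as crude percentages of children, with no child-time and no split at 24 months CA, although entry and exit ages vary

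*Protocol*

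**What the plan says.** **Age pattern.** Protocol 1.1.1 says that chronic respiratory morbidity after discharge involves "frequent emergency room visits or hospital readmissions, especially during the first 2 years of life". Protocol 8.2.3 makes an event serious if it "Requires inpatient hospitalization or prolongation of existing hospitalization", with an exception for elective or previously scheduled surgery.

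**Entry.** Protocol 3.1 sets the default for children who complete the parent study: "the initial visit in Study SHP607-203 should coincide with the final visit of Study SHP607-202 at 12 months CA +2 weeks". If that visit is missed, "the subject may still be enrolled until 24 months CA +6 weeks" (Protocol 3.1 and Table 1, footnote b).

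**Exit.** Protocol 3.1 plans follow-up to 5 years CA. SAP 3.1 reports that the study is terminated early, that fewer than 10% of the planned children enrolled, and that few reached the 5-year assessments.

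**Window.** Protocol 8.1: "All AEs described above are collected from the time the informed consent is signed until the defined follow-up period stated in Section 3.2".

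**Tables.** SAP 7.1 gives an overall AE summary and breakdowns such as "By system organ class (SOC) and PT for all AEs", each by arm and overall, as children affected and (except by maximum severity) event counts. SAP 9.1 makes the number of children in the arm the denominator. Neither section mentions child-time, an exposure-adjusted rate or an age band.

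**Parent study.** SAP 3.1 says that in Amendment 2 of Study 202 "the study design was updated to include a follow-up period until 24 months CA", and gives this as the reason for terminating Study 203.

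**The concern.** A crude percentage of children with an SAE depends on how long each child was watched and at what ages. A child who enters at 12 months CA is observed through the second year of corrected age; one who enters at the latest permitted age is not. A child who leaves at 3 years CA has less time to record an event than one who leaves at 5. The planned tables treat these children as equivalent.

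Two things are at stake. First, enrolment in Study 203 comes after treatment in an open-label parent study, so randomisation in Study 202 does not guarantee that entry and exit ages are balanced across arms. An arm with later entrants or earlier exits would show fewer SAEs for that reason alone. Second, the study asks about long-term safety, and no described table shows what happened after 24 months CA. SAP 6 drops all efficacy analysis, so these safety tables carry the only primary objective (SAP 2.1) that is still analysed.

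**Working it through.** The plan has no sample size, power or SAE rate to reproduce. The check asks how far crude percentages can move when the event rates are identical in every arm.

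**Inputs from the documents**
- Entry from 12 months CA to 24 months CA + 6 weeks: a spread of 1 + 6/52.18 = 1.11 years (Protocol 3.1).
- Possible follow-up to 5 years CA: 5 − 1 = 4.0 years for the earliest entrant, and 3 − 0.115 = 2.9 years for the latest.
- Enrolment below 10% of 477 (SAP 3.1): at most 47 children, or 47/3, about 16 per arm if evenly spread.
- Gestational age 23 weeks + 0 days to 27 weeks + 6 days (Protocol 1.3).

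**Assumptions, not in the documents**
- SAE rate before 24 months CA, r1: 0.2, 0.4 or 0.6 per child-year.
- SAE rate afterwards, r2: equal to r1, half of it or a quarter of it.
- Common exit at 2.5, 3 or 5 years CA.
- Term taken as 40 weeks.

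**Formula.** P(at least one SAE) = 1 − exp(−(r1·t1 + r2·t2)), where t1 and t2 are the years observed before and after 24 months CA.

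**Entry age, with r1 = 0.4 and r2 = 0.2**
- Exit at 5 years CA, entry at 12 months: 1 − exp(−(0.4×1 + 0.2×3)) = 63%. Latest entry: 1 − exp(−0.2×2.885) = 44%.
- Exit at 3 years CA: 1 − exp(−0.6) = 45%, against 1 − exp(−0.2×0.885) = 16%.
- Over the whole assumed grid, the gap between the earliest and latest entrant is 9 to 43 points. It does not need a falling rate: with r1 = r2 = 0.4 and exit at 3 years CA it is 55% against 30%.

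**Exit age, same rates, entry at 12 months CA.** Exit at 2, 3, 4 and 5 years CA gives 33%, 45%, 55% and 63%. Exit age matters as much as entry age.

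**Effect on an arm comparison.** Let one arm have 30% latest entrants and the other none.
- With r1 = 0.4, r2 = 0.2 and exit at 3 years CA, the mixed arm has 0.7×45.1% + 0.3×16.2% = 36.4%, a spurious gap of 8.7 points.
- Over the grid the gap is 2.6 to 13.0 points. It is zero when the arms have the same entry mix and the same exit ages.
- The 95% half-width in the same example is 1.96 × √[(0.451×0.549 + 0.364×0.636)/16] = 34 points; over the grid it is 21 to 35.
- A 30-point imbalance is itself generous. With 15% late entrants overall, the 95% chance limit at 16 per arm is 1.96 × √(2×0.15×0.85/16) = 25 points.

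**Would one overall rate per child-year be enough?** Not if the rate falls with age. With r1 = 0.4 and r2 = 0.2, earliest against latest entrants show 0.25 against 0.20 per year at exit at 5 years CA, and 0.30 against 0.20 at exit at 3 years CA. Rates within each age band return r1 and r2 whatever the entry age.

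**Events after 24 months CA.** For entry at 12 months CA their expected share is r2(x − 2)/(r1 + r2(x − 2)), with x the exit age in years. Over the grid this runs from 11% (exit at 2.5 years) to 75% (exit at 5 years). A pooled count gives no indication of which applies.

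**The case against.** **By-arm bias is not shown.** A reader might infer that the SAE percentages will follow age at entry. That needs entry or exit ages to differ between arms, and no document shows this. Entry at 12 months CA is the default and later entry an allowance. This objection stands.

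**The effect is small against noise.** The spurious gaps above lie inside the sampling error at this size, and SAP 7.1 plans no between-arm test or interval for AEs. This stands: no planned inference is overturned.

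**The information is not wholly hidden.** SAP 5.1 summarises visits completed by arm and lists study completion by child. SAP 5.2 summarises and lists CA at enrollment and gestational age. SAP 7.1 lists all AEs, with a separate SAE listing. With at most 47 children, a reader could rebuild much of the split if those listings carry dates. The table and listing specifications are in a separate document (SAP 1), so this cannot be settled here. It limits the point to the tables as the SAP describes them; rebuilding child-time per band by hand is a poor substitute for reporting it.

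**The age statement should not be stretched.** Protocol 1.1.1 concerns respiratory morbidity, not all SAEs, and does not say that events are confined to the first 2 years. Those are years of life: with 40 − 23 = 17 to 40 − 27.86 = 12.14 weeks of prematurity, at 4.345 weeks per month, they end at about 20.1 to 21.2 months CA. The cut at 24 months CA rests on the study's visit structure and the parent study's revised follow-up, not on that sentence.

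**Overlap with Study 202 is not established.** A reader might infer from SAP 3.1 that everything before 24 months CA duplicates Study 202 data. SAP 3.1 says only that the parent design was extended. It does not say that Study 203 children were followed under that amendment, and the Study 203 protocol places its first visit at the final Study 202 visit. For some children Study 203 may be the only source between 12 and 24 months CA.

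**Conclusion.** The point holds as a reporting weakness, and the change is a cheap improvement. SAP 7.1 and 9.1 use the number of children as denominator over one window of unequal length and unequal ages, so by-arm SAE percentages can differ without a drug effect if entry or exit ages differ between arms. This is a risk that has not been shown to have occurred. In the illustration its size is about 3 to 13 points, against a half-width of 21 to 35 points at about 16 per arm. Those figures rest on assumed rates, an assumed 30% against 0% split of latest entrants, and arms of equal size.

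The second part does not depend on any imbalance: no table described in the SAP separates events after 24 months CA from earlier ones, although long-term safety is the one primary objective still analysed. The stronger readings, that the arm comparison is biased or that the earlier period merely repeats Study 202, go beyond the documents.

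**What to change.** Keep the pooled tables in SAP 7.1 and make these additions:

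1. By arm, repeat the overall AE summary, the SAE table and the targeted medical events by corrected age at onset: before 24 months CA, and 24 months CA or later.
2. In each band, give the number of children observed and the child-time observed, from consent or the start of the band to exit or the end of the band. This handles entry age and exit age together.
3. Show corrected age at onset in the AE and SAE listings.
4. Flag events whose band depends on an imputed start date. SAP 9.2.1.1 moves partial dates after the consent year to 1 January, or to the first of the month when only the day is missing and the month is later than consent, which can pull events into the younger band.
5. Do not describe the first band as also covered by Study 202 unless those children were in fact followed under its Amendment 2.

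The cost is SAP wording and some repeated tables. Onset dates are already collected and CA at enrollment is already derived, so no new data are needed. The downside is sparse cells, which is acceptable in descriptive tables; SOC and PT detail by band can be limited to SAEs.
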